5.9. Study Withdrawal

Study withdrawal (referred to in the protocol as dropout), is the combination of subjects who withdraw, are lost to follow-up (LTFU), or die during the study

Study withdrawal is defined as any subject who withdraws from the study prior to the analysis visit of interest (e.g. Week 52, Week 64, Week 104) and does not have a visit within ± 28 days of the target analysis visit date (excluding follow up visits).

This rule is applied consistently across all efficacy endpoints. The assessment of whether or not a subject had a visit within the ± 28 day of an analysis visit (e.g. Week 52) is performed at the domain level [e.g., a subject who had visit within 28 days for SLEDAI-2K but not a SLICC ACR assessment would be assessed on their observed data for SLEDAI-2K but would be considered withdrawn (non-responder) in SLICC ACR assessment].

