7.1. Primary Efficacy Analyses

7.1.1. Endpoint / Variables

The protocol defined primary endpoint is the proportion of participants with a state of disease control defined as a SLEDAI-2K score ≤ 2 (IBA), achieved without immunosuppressants and with corticosteroids at a prednisone equivalent dose of ≤ 5 mg/day at Week 52 (Protocol Section 4).

The protocol Section 10.4.1 Efficacy analysis then clarifies that:

For participants who withdraw prematurely from study treatment and for who subsequent collection of data is not possible, it will be assumed for the primary analysis that they are treatment failures. A dropout/treatment failure = non-responder (DO/TF=NR) analysis will be used .

Hence when adopting the ICH Estimands and Sensitivity Analysis in Clinical Trials E9 R1 addendum terminology, this endpoint is defined as:

| Disease Control |
|--|
| 
Responder:
 
 • SLEDAI-2K score ≤ 2 (IBA); and • Not a TF at the current or any prior visit (TF includes consideration of corticosteroids and immunosuppressants); and • Did not withdraw from the study prior to the visit 
Non-Responder:
 
 • SLEDAI-2K score > 2 (IBA); or • TF at the current or any prior visit (TF includes consideration of corticosteroids and immunosuppressants); or • Withdrew from the study prior to visit (which includes study withdrawal, lost to follow-up and death) |
| 
The derivation of SLEDAI-2K score is provided in Section 15.6.3, treatment failures are defined in Section 15.6.15. and withdrawal from the study prior to Week 52 in Section 5.9.
 |
| 
Note: Discontinuation of study investigational product (belimumab or rituximab) is NOT a component of this endpoint, subjects who discontinue investigational product will only be non-responders if they also meet one of the criteria above.
 |

Note this clarification of notation does not change the protocol-specified primary analysis.

The analysis of the primary endpoint of Arm A vs Arm B will use data from treatment Arms A, and B only.

An exploratory analysis of the relative performance of Arm B vs. Arm C will also be conducted, using data from Arms B and C only.

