7.1.6. Tipping Point Analysis

Tipping point analyses will be performed for the primary endpoint if the endpoint is statistically significant and it is plausible that missing data caused by study withdrawal could alter the conclusions of the analysis (treatment p-value is ≤ 0.05 and > 0.001). If the tipping point analyses are needed, they will be performed shortly after the Statistical Analysis Complete milestone has been met and will be presented in the clinical study report.

The tipping point analyses will be based on the Intent-to-Treat population. Only the subjects in the belimumab plus placebo, and belimumab plus rituximab arms will be considered.

For the primary analysis, subjects for whom the Week 52 disease control status cannot be determined due to study withdrawal (including lost to follow-up, and death) are imputed as non-responders. In contrast, the missing data due to study withdrawal in the tipping point analysis is evaluated using multiple imputation methods, by simulating all combinations of response probability in the treatment arms independently.

The first tipping point analysis will use the Hybrid strategy (as described in Section 7.1.4 as per the primary estimand). If a subject's study withdrawal is subsequent to treatment failure the subject will still be considered as a non-responder, i.e. the non-responder assumption will only be varied for withdrawn subjects that were not treatment failures.

The second tipping point analysis will use the treatment policy strategy (Section 7.1.4). In this approach, treatment failure data is ignored, i.e. the non-responder assumption is varied for all withdrawn subjects regardless of treatment failures.

The tipping point analyses will not consider covariates. However, if the conclusions of the primary analysis adjusting for covariates differ from the conclusions of the unadjusted analysis, a post hoc analysis assessing the impact of covariate adjustment in the tipping point analyses may be performed.

[figure not shown]
The following multiple imputation method will be implemented:

1. For subjects in Arm A (belimumab plus placebo) and Arm B (belimumab plus rituximab) with missing Bernoulli outcomes, a grid of the probability of response varying from 0.025 to 0.975 by 0.025 will be created. This will create all combinations, from low to high response probability, for subjects with a missing response.
2. For a given of probability (e.g., 0.025 for Arm A, 0.500 for Arm B)

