- with corticosteroids at a prednisone equivalent dose of $\leq 5\text{mg/day}$, in the absence of higher doses that could be attributable to the COVID-19 pandemic

The full MITT population will be used, with the following attributes:

- A strategy that matches the primary analysis (Hybrid) will be used for the following Intercurrent Events to classify the subject as a Non-Responder:
 - Study Withdrawal (includes Lost to Follow Up) that occurs prior to the COVID-19 environment onset date
 - Treatment Failure (includes consideration of corticosteroids and immunosuppressants) that occurs prior to the COVID-19 environment onset date
 - Death that occurs at any time
- A hypothetical strategy will be used for any subject who has their Week 52 assessment scheduled to be on or after the COVID-19 environment onset date, who has not been classified as a Non-Responder using the strategy above, and has any of the following Intercurrent Events on or after the COVID-19 onset date:
 - Study Withdrawal (includes Lost to Follow Up)
 - Treatment Failure (includes consideration of corticosteroids and immunosuppressants)
 - Missing SLEDAI-2K score (IBA)

The response status for these subjects will be treated as a missing value and will be assumed to be Missing At Random (MAR). It will be imputed using Multiple Imputation methods, which take into account the subjects baseline characteristics and their existing pre-COVID-19 data.
- Discontinuation of study investigational product (belimumab or rituximab) is NOT a component of this endpoint.

| |
|--|
| Imputation of Missing Data |

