7.1.7.4. Graphical Representation of the Additional Analyses

Table 3 shows a graphical representation of specific scenarios for individual subjects, in terms of their completion status or any Intercurrent Events, and the timing of them in relation to the COVID-19 environment onset date (Section 15.6.16). The way in which the data for subjects in each scenario will be used is presented for the primary analysis, plus each of the three pre-specified additional analyses to investigate the COVID-19 pandemic.

Table 3 Graphical Representation of the Additional Analyses

| COVID-19 environment Onset date | | Description | Primary Analysis Hybrid | COVID Attributed | COVID Environment | Pre- COVID |
|------------------------------------|---------------|--|----------------------------|---------------------|----------------------|---------------|
| X—————0 Comp. | | Subject Completes Week 52 prior to onset date | R/NR | R/NR | R/NR | R/NR |
| X—————0 WD/Death | | Subject had scheduled Week 52 prior to COVID-19 environment onset date, but Withdraws / LTFU / Dies prior to COVID-19 environment onset date | NR | NR | NR | NR |
| X—————0 TF | | Subject had scheduled Week 52 prior to onset date, but has Treatment Failure prior to onset date | NR | NR | NR | NR |
| | X—————0 Comp. | Subject Completes on or after COVID-19 environment onset date | R/NR | R/NR | Imputed | Excluded |
| WD/Death | X—————0 | Subject had scheduled Week 52 on or after onset date, but Withdraws/Dies prior to onset date | NR | NR | NR | Excluded |
| TF | X—————0 | Subject had scheduled Week 52 on or after onset date, but has Treatment Failure prior to onset date | NR | NR | NR | Excluded |

| | | | | | | |
|---|--------------------|--|----|---------|---------|----------|
| X | 0 WD | Subject Withdraws on or after onset date | NR | Imputed | Imputed | Excluded |
| X | 0 Death | Subject Dies on or after onset date | NR | NR | Imputed | Excluded |
| X | 0 TF | Subject has Treatment Failure on or after onset date | NR | Imputed | Imputed | Excluded |

Comp. = Completed; WD = Study Withdrawal (includes Lost to Follow Up); TF = Treatment Failure (includes consideration of corticosteroids and immunosuppressants); R/NR = Responder/Non-Responder based on SLEDAI-2K criteria; NR = Non-Responder

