7.9.4. Strategy for Intercurrent (Post-Randomization) Events

A hypothetical strategy will be used to estimate what the treatment effect would have been had the subjects not withdrawn from the study . Data collected after TF will be used in the analysis.

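### The tipping-point analyses let participants who died be simulated as responders, although death is a known non-response under the endpoint definition

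*SAP*

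**What the plan says.** SAP 5.9 defines study withdrawal so that it "is the combination of subjects who withdraw, are lost to follow-up (LTFU), or die during the study". In the primary endpoint (SAP 7.1.1) a participant is a non-responder if he or she "Withdrew from the study prior to visit (which includes study withdrawal, lost to follow-up and death".

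SAP 7.1.6 repeats this for the primary analysis: participants whose Week 52 status is unknown "due to study withdrawal (including lost to follow-up, and death) are imputed as non-responders". It then departs from that rule: "the missing data due to study withdrawal in the tipping point analysis is evaluated using multiple imputation methods, by simulating all combinations of response probability". Under the first analysis (Hybrid strategy) the one exemption is prior treatment failure: "the non-responder assumption will only be varied for withdrawn subjects that were not treatment failures". In the second (treatment policy strategy) the assumption is varied for every withdrawn participant. The grid runs from 0.025 to 0.975 in steps of 0.025, separately for Arms A and B, with 1000 imputations per cell.

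Addendum 1 Section 2.3 returns to this text and adds participants with missing or partial non-informative SLEDAI-2K data. It does not exempt deaths.

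COVID Attributed (SAP 7.1.7.1) takes death out of the imputed set. Its list of events that make a participant a non-responder includes "Death that occurs at any time".

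**The concern.** A tipping-point analysis asks how far the unknown outcomes would have to depart from the primary assumption before the conclusion changes. That makes sense for someone who left the study alive, because the Week 52 state exists but was not observed. For someone who died before Week 52 nothing is unknown: the endpoint definition already classes that person as a non-responder.

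Putting deaths on the grid fills the heat map with scenarios that cannot occur. The protocol's risk assessment (3.3.1) foresees more complete B-cell depletion and more serious infection with the combination, so deaths need not be balanced between the arms. The point at which the result appears to tip could then depend partly on impossible outcomes.

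**Working it through.** **1. Tracing a death through the rules (no treatment failure beforehand)**

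| Analysis | SAP section | Handling |
|---|---|---|
| Primary (Hybrid) | 7.1.1, 7.1.4 | Non-responder |
| Composite; Treatment Policy | 7.1.4 | Non-responder |
| COVID Attributed | 7.1.7.1 | Non-responder at any time |
| Tipping point, first (Hybrid) | 7.1.6 | Response probability 0.025 to 0.975 |
| Tipping point, second (Treatment Policy) | 7.1.6 | Response probability 0.025 to 0.975 |

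A death after treatment failure stays a non-responder in the first tipping-point analysis but not in the second. The sentence that sets up the imputation does not itself name death. The link is the sentence before it, together with 5.9.

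**2. The grid.** From 0.025 to 0.975 by 0.025 there are 39 values per arm, so 39 × 39 = 1521 cells. Zero is not among them.

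**3. Size per death.** Arm sizes are the planned 70 and 140 (protocol 10.2). With d deaths and grid probability p, the expected shift in an arm's response rate is d × p / n.

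| Deaths | p | Arm B (n = 140) | Arm A (n = 70) |
|---|---|---|---|
| 1 | 0.10 | 0.07 points | 0.14 points |
| 1 | 0.975 | 0.70 points | 1.39 points |
| 3 | 0.975 | 2.09 points | 4.18 points |
| 5 | 0.975 | 3.48 points | 6.96 points |

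The numbers of deaths are assumed.

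**4. Effect on a p-value near the boundary.** The plan gives no figure for deaths. Its minimum detectable effect (protocol 10.2: about 11 points over a 10% control rate) serves as an anchor. With 7/70, the smallest Arm B count giving likelihood-ratio p < 0.05 is 29/140, a difference of 10.7 points with p = 0.044; 28/140 gives 0.057.

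Take 7/70 versus 30/140. The pooled rate is 37/210 = 0.1762, and G² = 2 Σ O ln(O/E).
- Arm A: 7 ln(0.1000/0.1762) + 63 ln(0.9000/0.8238) = 1.61
- Arm B: 30 ln(0.2143/0.1762) + 110 ln(0.7857/0.8238) = 0.66
- G² = 2 × 2.27 = 4.54, so p = 0.033

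Counting deaths as certain responders:

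| Arm A | Arm B | p |
|---|---|---|
| 7/70 | 31/140 (one Arm B death) | 0.025 |
| 7/70 | 32/140 (two) | 0.018 |
| 7/70 | 33/140 (three) | 0.014 |
| 8/70 (one Arm A death) | 30/140 | 0.067 |

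These are upper bounds for the stated number of deaths. The actual procedure draws binomially, uses a Mantel-Haenszel test and pools by Rubin's rules.

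**5. A closer approximation.** Assume 7 living participants missing in Arm A and 14 in Arm B, and combine binomial imputation with a Wald/Rubin p-value. With both arms at 0.10 (the setting that 7.1.6 calls plausible, if the observed Arm A rate is 10%), adding three Arm B deaths moves p from 0.032 to 0.029. At 0.50 for Arm A and 0.025 for Arm B, p is about 0.25 with or without them.

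**The case against.** The strongest reply is that this is narrow and changes little. The primary analysis and the Composite and Treatment Policy analyses all count death as non-response. The tipping point is conditional on 0.001 < p ≤ 0.05. It is read from the corner adverse to Arm B, where an Arm B death has probability 0.025 and is close to non-response anyway. All of that stands, and it limits the size of the point. It does not make the rule right, because in that same corner Arm A deaths carry high probabilities and make the check harsher than any possible outcome.

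A reader might infer that the rule favours whichever arm has more deaths, and so flatters the combination. The documents do not support that. The arms vary independently, and the illustration moves p down for an Arm B death and up for an Arm A death.

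A reader might also want the same change in COVID Environment (7.1.7.2), where Table 3 marks the row "Subject Dies on or after onset date" as imputed, and in the continuous endpoints, where 7.9.4 says "A hypothetical strategy will be used to estimate what the treatment effect would have been had the subjects not withdrawn from the study" and 9.1 also imputes after withdrawal. Those follow from declared estimands. COVID Environment makes the onset date the intercurrent event and also imputes completers with observed scores and treatment failures after that date. Keeping only deaths as observed would mix two estimands. The continuous analyses openly adopt a hypothetical strategy. Changing either is a choice of estimand, not a correction.

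**Conclusion.** The point holds for the tipping-point analyses only. As written, SAP 7.1.6 and Addendum 1 Section 2.3 simulate a known non-response as a possible response, against the endpoint definition and against COVID Attributed.

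One death shifts the expected response rate by at most 0.70 points in Arm B or 1.39 in Arm A. Near the significance boundary that could move a cell across 0.05 in either direction; with few deaths it will usually change nothing. This rests on the planned arm sizes and assumed numbers of deaths and missing outcomes.

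It does not touch the primary result. It may also never have been applied: Addendum 2 adopts the abridged end-of-study outputs that SAP 3.2 reserves for the case of no treatment benefit at Week 52, and its list omits the Week 64 and Week 104 tipping-point tables. The documents do not say whether the Week 52 analysis was triggered.

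**What to change.** In SAP 7.1.6 and Addendum 1 Section 2.3, restrict the varied set to living participants whose outcome is undetermined: withdrawal, loss to follow-up, or a missing or partial non-informative score. Hold as non-responders, in every grid cell of both analyses, the deaths that 5.9 classes as withdrawal before the visit.

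The cost is a few words and one condition in the program. Dates of death are already used in the time-to-event rules (7.7.5), so no new data are needed. Since the first database lock has passed, a Week 52 rerun would be post hoc and should be labelled so. If that analysis was run, add this version or disclose in the report how deaths were handled.

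For COVID Environment and the continuous analyses in 7.9 and 9.1 no change is required. At most, add a sentence on why death is handled differently there from 7.1.7.1.

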7.1.7.2. COVID Environment – Observed Data Until the COVID-19 Pandemic

The second additional analysis assumes that all data after the COVID-19 environment onset date may either be missing due to the pandemic or affected by the pandemic. There may be intangible ways that

the data may have been affected even if it has been collected, therefore this analysis accepts that we cannot distinguish between affected and unaffected data after the COVID-19 environment onset date.

A Hypothetical estimand will be used to estimate the treatment effect had the COVID-19 pandemic not occurred. The difference in response rates between Arm A and Arm B at Week 52 will be assessed for subjects who:

- achieve a SLEDAI 2K-score ≤ 2 (IBA),
- without immunosuppressants and
- with corticosteroids at a prednisone equivalent dose of ≤ 5 mg/day and
- in the absence of any Intercurrent Events that could be attributable to the COVID-19 pandemic, based on the COVID-19 environment onset date.

The full MITT population will be used, with the following attributes:

- A strategy that matches the primary analysis (Hybrid) will be used for the following Intercurrent Events to classify the subject as a Non-Responder:
 - Study Withdrawal (includes Lost to Follow Up and death) that occurs prior to the onset date
 - Treatment Failure (includes consideration of corticosteroids and immunosuppressants) that occurs prior to the onset date
 -
- A hypothetical strategy using the COVID-19 environment onset date as the Intercurrent Event will be used for any subject who has their Week 52 assessment scheduled to be on or after the COVID-19 environment onset date, who has not already been classified as a Non-Responder using the strategy above. The response status for these subjects will be treated as a missing value and will be assumed to be Missing At Random (MAR). It will be imputed using Multiple Imputation methods, which take into account the subjects baseline characteristics and their existing pre-COVID data.
- Discontinuation of study investigational product (belimumab or rituximab) is NOT a component of this endpoint.

The statistical methods will match the first additional analysis (Section [7.1.7.1](#)) [T12.41].

7.1.7.3. Pre-COVID – MITT Population Prior to the COVID-19 Pandemic

The third additional analysis will use the “MITT Week 52 prior to COVID-19” analysis population. This will assess the treatment difference on the subset of subjects who completed Week 52 before the COVID-19 environment onset date and hence have no possible COVID-19 impact on any of their assessments.

A Hybrid estimand will be used to estimate the treatment effect in the population of subjects for which the COVID-19 pandemic not occurred. The difference in response rates between Arm A and Arm B at Week 52 will be assessed for subjects who complete Week 52 prior to the COVID-19 environment onset date and who:

- achieve a SLEDAI 2K-score ≤ 2 (IBA),
- without immunosuppressants and
- with corticosteroids at a prednisone equivalent dose of ≤ 5 mg/day.

The “MITT Week 52 prior to COVID-19” population will be used, with the following attributes:

- A strategy that matches the primary analysis (Hybrid) will be used for the following Intercurrent Events to classify the subject as a Non-Responder:
 - Study Withdrawal (includes Lost to Follow Up and Death)
 - Treatment Failure (includes consideration of corticosteroids and immunosuppressants)
- Discontinuation of study investigational product (belimumab or rituximab) is NOT a component of this endpoint.

The statistical methods will match the primary analysis (Section 7.1.5) for the endpoint definition, derivation, model specification, model checking and diagnostics and the model results presentation [T12.42].

7.1.7.4. Graphical Representation of the Additional Analyses

Table 3 shows a graphical representation of specific scenarios for individual subjects, in terms of their completion status or any Intercurrent Events, and the timing of them in relation to the COVID-19 environment onset date (Section 15.6.16). The way in which the data for subjects in each scenario will be used is presented for the primary analysis, plus each of the three pre-specified additional analyses to investigate the COVID-19 pandemic.

Table 3 Graphical Representation of the Additional Analyses

| COVID-19 environment Onset date | | Description | Primary Analysis Hybrid | COVID Attributed | COVID Environment | Pre- COVID |
|------------------------------------|---------------|--|----------------------------|---------------------|----------------------|---------------|
| X—————0 Comp. | | Subject Completes Week 52 prior to onset date | R/NR | R/NR | R/NR | R/NR |
| X—————0 WD/Death | | Subject had scheduled Week 52 prior to COVID-19 environment onset date, but Withdraws / LTFU / Dies prior to COVID-19 environment onset date | NR | NR | NR | NR |
| X—————0 TF | | Subject had scheduled Week 52 prior to onset date, but has Treatment Failure prior to onset date | NR | NR | NR | NR |
| | X—————0 Comp. | Subject Completes on or after COVID-19 environment onset date | R/NR | R/NR | Imputed | Excluded |
| WD/Death | X—————0 | Subject had scheduled Week 52 on or after onset date, but Withdraws/Dies prior to onset date | NR | NR | NR | Excluded |
| TF | X—————0 | Subject had scheduled Week 52 on or after onset date, but has Treatment Failure prior to onset date | NR | NR | NR | Excluded |

| | | | | | | |
|---|--------------------|--|----|---------|---------|----------|
| X | 0 WD | Subject Withdraws on or after onset date | NR | Imputed | Imputed | Excluded |
| X | 0 Death | Subject Dies on or after onset date | NR | NR | Imputed | Excluded |
| X | 0 TF | Subject has Treatment Failure on or after onset date | NR | Imputed | Imputed | Excluded |

Comp. = Completed; WD = Study Withdrawal (includes Lost to Follow Up); TF = Treatment Failure (includes consideration of corticosteroids and immunosuppressants); R/NR = Responder/Non-Responder based on SLEDAI-2K criteria; NR = Non-Responder

